9.4 Assessment of the Primary Endpoint

9.4.1 Group 1

The primary endpoint, defined as the proportion of patients able to be contacted and willing to participate in patient assessment #1, will be determined based on up to three contact attempts with the patient over the course of 2 weeks. Patients will be counted as meeting the primary endpoint if they complete the entirety of assessment #1. A brief message stating the research assistant's name and affiliation with the anticoagulation clinic and asking the patient to call back at the earliest convenience will be left for the patient if they do not answer the phone during any of the three contact attempts.

9.4.2 Group 2

N/A

9.5 Assessment of the Secondary Endpoint

9.5.1 Group 1

The proportion of patients who received all implementation strategies to which they were assigned will be determined by EHR chart review in the 6 months following the trial.

9.5.2 Group 2

N/A

9.6 All Other Study Assessments – Group 1

Assessment of all exploratory study endpoints will be performed by a research assistant using chart review or semi-structured interview assessments conducted by phone or zoom call with patients,

clinicians, and anticoagulation clinic staff. There will be no assessments that require physical exams, radiology, biological specimens or laboratory evaluations.

9.6.1 Chart Review for Randomized Patients

For each patient participating in the trial, review of the electronic health record will be performed by a research team member to ascertain documentation of delivery of the quality improvement strategy components, documentation of medication changes, documentation of contact between clinicians and anticoagulation staff, appropriateness of antiplatelet therapy prior to and after the QI strategies, as well as other variables required for evaluation of exploratory outcomes.

To evaluate the appropriateness of antiplatelet therapy for randomized patients, a study team member who has training in internal medicine will conduct a detailed chart review for each patient. The team member will determine, first, whether the antiplatelet therapy initially prescribed was either probably appropriate, probably inappropriate, or uncertain, and second, whether continuation or discontinuation of antiplatelet therapy at the time of chart review was either probably appropriate, probably inappropriate, or uncertain.

9.6.2 Chart Review for All Anticoagulation Clinic Patients who Meet Eligibility Criteria at Baseline

For all patients who are enrolled with the anticoagulation clinic monitoring service at Michigan Medicine at the time of study initiation, review of the electronic health record will be performed by a research team member to determine (1) the total number of patients who meet eligibility criteria for the study, (2) the proportion of patients who met eligibility criteria at study initiation who discontinued warfarin therapy or were closed to the service during the study period, and (3) the number of patients who were eligible at study initiation and made one of the two medication-optimization changes during the study period. This data will provide necessary information about the number of patients who may require medication optimization in the future full-scale trial and also about the use of evidence-based strategies to reduce upper GI bleeding risk in usual practice without use of the implementation strategies being tested. This data would be obtained using workbench reports developed specifically to identify patients at high-risk for upper GI bleeding and through review of the electronic health record for additional data when needed. As these assessments are of patients who were not randomized to a QI strategy in this pilot trial and this data will be used solely for assessing feasibility of a future larger scale trial, we are seeking a waiver of consent and a waiver of HIPAA authorization to obtain this data.

9.7 All Other Study Assessments – Group 2

Assessment of the primary exploratory endpoint will be completed by the research team using semi-structured interview assessments with primary care clinicians who received one of the clinician-level strategies for a patient they care for. Assessment of all secondary exploratory study endpoints will be performed by a research assistant using chart review. There will be no

assessments that require physical exams, radiology, biological specimens or laboratory evaluations.

9.7.1 Chart Review for Randomized Patients

For each patient participating in the trial, review of the electronic health record will be performed by a research team member to ascertain documentation of delivery of the quality improvement strategy components, documentation of medication changes, documentation of contact between clinicians and anticoagulation staff, as well as other variables required for evaluation of exploratory outcomes.

10 ADVERSE EVENTS

Since this trial constitutes a quality improvement trial intended to improve the use of evidence-based practices to reduce bleeding in patients using CAT, and since all decisions regarding changes in drug treatment will be made by patients' own clinicians as part of usual care, the study will not proactively monitor for adverse events. No experimental drug is being investigated. However, any adverse events that are identified will be logged in an adverse event database.

11 STATISTICAL CONSIDERATIONS

11.1 Sample Size Determination

11.1.1 Group 1

The sample size was determined in consideration of the primary endpoint, which is the rate of participant recruitment and participation in assessment #1. With a sample size of 40, we will be able to estimate a recruitment rate of 80% to within a 95% confidence interval of +/- 13%, using normal approximation to the binomial calculation.

11.1.2 Group 2

N/A

11.2 General Statistical Approach

11.2.1 Group 1

For the primary and secondary analyses, all participants who undergo randomization will be analyzed. Proportions with confidence intervals will be calculated.

11.2.2 Group 2

For the primary and secondary exploratory analyses, all participants who undergo randomization will be analyzed. Proportions with confidence intervals will be calculated.

11.3 Descriptives

11.3.1 Group 1

We will calculate descriptive statistics (means and proportions) for all patient variables.

11.3.2 Group 2

We will calculate descriptive statistics (means and proportions) for all patient variables obtainable through chart review.

11.4 Hypotheses

11.4.1 Group 1

We hypothesize that the rate of participant recruitment and participation in assessment 1 (the primary endpoint) will exceed 66%.

Similarly, we hypothesize that the rate of delivery of intended quality improvement strategies will exceed 66%.

11.4.2 Group 2

N/A for qualitative primary exploratory endpoint.

11.5 Analysis of the Primary Endpoint(s)

11.5.1 Group 1

We will calculate the proportion of randomized patients that complete the patient assessment at week 5. We will estimate the confidence interval using the normal approximation to the binomial distribution. We will accept this hypothesis if the two-sided confidence interval ($\alpha=0.05$) for the primary endpoint excludes 0.66.

11.5.2 Group 2

Qualitative analysis will be performed to explore clinician perceptions of the intervention strategies for the primary exploratory endpoint.

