Study Population:	
Group 1: Quality improvement strategy components will be directed at both patients and clinicians. Patients will be eligible for inclusion if they are prescribed warfarin and an antiplatelet drug without a PPI and are enrolled in the Michigan Medicine anticoagulation monitoring service. See section 6.1 for additional inclusion and exclusion criteria. Clinicians will be eligible for inclusion if they are the clinician of record for a patient meeting inclusion criterion (i.e., the clinician who receives routine communications from the anticoagulation service), or if they are a cardiologist who has had a visit with the patient in the prior year. We anticipate including 12 clinicians and 51 patients. All participating anticoagulation clinic staff, who will deliver the QI strategies, will also be included to assess their perceptions of program feasibility and acceptability.
 
Group 2: Quality improvement strategy components will be directed at both patients and clinicians. Patients will be eligible for inclusion if they are prescribed warfarin and an antiplatelet drug without a PPI, are enrolled in the Michigan Medicine anticoagulation monitoring service, and have a physician in Group 2 as their clinician of record for the anticoagulation clinic. See section 6.1 for additional inclusion and exclusion criteria.

Clinicians will be eligible for inclusion if they are the clinician of record for a patient meeting inclusion criterion (i.e., the clinician who receives routine communications from the anticoagulation service), and are a primary care specialist. We anticipate including 8 primary care clinicians and 8-16 of their patients.

Study Description:

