use of one of the evidence-based practices but not the other, which may lead to suboptimal care. Clinicians may also have concerns about provoking a cardiovascular event when deprescribing antiplatelet drugs, and about possible PPI adverse effects when initiating a PPI [[name] AFM, in press].

There is a critical need for implementation strategies to improve medication optimization for upper GI bleeding risk reduction in patients prescribed CAT. Importantly, to ensure the most appropriate care, any implementation strategy should simultaneously address both evidence-based practices, determining first the appropriateness of antiplatelet therapy, then of PPI gastroprotection. Previous one- or two- component clinician-facing interventions aimed at improving use of PPI gastroprotection (including decision support tools, electronic alerts, audit and feedback, and clinician education) have had limited success ¹⁰⁻¹³. Several European studies that have tested multi-component interventions involving professional education, incentive payments, clinician feedback, and pharmacist support have effectively reduced the proportion of high-risk patients without gastroprotection (odds ratios 0.55-0.72) ¹⁵⁻¹⁷. However, such multicomponent strategies are resource intensive and challenging to implement in the fragmented US healthcare system. There have been limited efforts to activate patients to enhance the quality of their care in this clinical domain ¹⁴.

As part of a quality improvement program through the Michigan Medicine anticoagulation service, three potential implementation strategies have been identified to improve the safety of patients using CAT, including clinician notification by electronic health record (EHR) message, a multi-faceted nurse facilitated process involving clinician notification + nurse facilitation, and activation of patients to discuss medication optimization with their clinicians using a newly developed guide. The anticoagulation clinic intends to undertake a clinic-wide randomized quality improvement trial in the near future to evaluate the effectiveness of these strategies. This protocol describes plans for a pilot randomized evaluation of the quality improvement project, focused on feasibility, which will provide essential information for planning the future quality improvement trial.

2.2 Objectives - Group 1

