6 STUDY POPULATION

6.1 Sample size

6.1.1 Group 1

The target sample size for group 1 in the pilot study is 40-51 patients cared for by 12 target clinicians. See sample size determination (below) for a justification of the size.

6.1.2 Group 2

The target sample size for group 2 is 8-16 patients cared for by 8 target clinicians who specialize in primary care.

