11.6 Analysis of the Secondary Endpoint(s)

11.6.1 Group 1

We will calculate the proportion of randomized patients that received all implementation components to which they were randomized in the appropriate time frame. We will estimate the confidence interval using the normal approximation to the binomial distribution. We will accept the hypothesis if the two-sided confidence interval (alpha=0.05) for the secondary endpoint excludes 0.66.

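### The 66% acceptance rule rests on a Wald interval whose lower limit is too high at n = 40 to 51; at the planning result of 32/40 it accepts when Wilson and exact intervals do not (minor)

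*Combined protocol and SAP*

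**What the plan says.** For Group 1, section 11.4.1 sets the primary hypothesis: "We hypothesize that the rate of participant recruitment and participation in assessment 1 (the primary endpoint) will exceed 66" percent. It sets the same threshold for delivery of the assigned strategies. Section 11.5.1 fixes the interval ("We will estimate the confidence interval using the normal approximation to the binomial distribution") and accepts the primary hypothesis if the two-sided interval at alpha 0.05 excludes 0.66. Section 11.6.1 uses the same method for the secondary endpoint: "We will accept the hypothesis if the two-sided confidence interval (alpha=0.05) for the secondary endpoint excludes 0.66".

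Section 11.1.1 justifies the size with the same approximation: at n = 40, "we will be able to estimate a recruitment rate of 80% to within a 95% confidence interval of +/- 13" percentage points. Section 6.1.1 states: "The target sample size for group 1 in the pilot study is 40-51 patients cared for by 12 target clinicians". The synopsis expects the upper end: "We anticipate including 12 clinicians and 51 patients". No score or exact interval, continuity correction or sensitivity analysis for the interval appears anywhere.

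**The concern.** A Wald interval is symmetric about the observed proportion. For a proportion near 80% with 40 to 51 patients the binomial distribution is skewed, and a better-calibrated interval reaches further down than up. The lower limit is the one compared with 66%, so the approximation errs towards acceptance.

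Two things are at stake. The rule should deliver the alpha that the plan states. And the one result that 11.1.1 works through should not count as success under one interval formula and not under the standard alternatives.

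**Working it through.** **Inputs.** n = 40 and a rate of 80%, i.e. 32/40 (11.1.1); n = 40 to 51 (6.1.1); threshold 0.66 (11.4.1); two-sided alpha 0.05, so z = 1.96 and 2.5% per tail (11.5.1, 11.6.1). Patients are treated as independent. The normal approximation is read as having no continuity correction, since none is mentioned.

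**1. The plan's own figure.** Wald half-width = z × √(p(1−p)/n) = 1.96 × √(0.8 × 0.2/40) = 1.96 × 0.0632 = 0.124. That is 12.4 points, which agrees with the stated 13 if rounded up.

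**2. Three intervals at 32/40.**
- Wald: 0.800 ± 0.124 = 0.676 to 0.924. Excludes 0.66, so accepts.
- Wilson: [p + z²/2n ± z√(p(1−p)/n + z²/4n²)] / (1 + z²/n) = (0.848 ± 0.133)/1.096 = 0.652 to 0.895. Includes 0.66.
- Clopper-Pearson: the 2.5% point of Beta(32, 9) and the 97.5% point of Beta(33, 8) = 0.644 to 0.909. Includes 0.66.

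The exact interval reaches 15.6 points below 80% and 10.9 above.

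**3. Smallest accepting count and error.** For each n, find the smallest count c whose lower limit exceeds 0.66. The error in the accepting direction is P(X ≥ c) for X ~ Binomial(n, 0.66); the chance of acceptance at a true 80% uses 0.80 instead. At n = 40, P(X ≥ 32) = 4.02% and P(X ≥ 33) = 1.71%. Selected sizes, in the order Wald / Wilson / exact:

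| n | c | Error at true 66% (%) | Acceptance at true 80% (%) |
|---|---|---|---|
| 40 | 32 / 33 / 33 | 4.02 / 1.71 / 1.71 | 59.3 / 43.7 / 43.7 |
| 42 | 33 / 34 / 35 | 5.60 / 2.59 / 1.05 | 67.6 / 53.1 / 37.8 |
| 45 | 36 / 36 / 37 | 3.02 / 3.02 / 1.30 | 58.8 / 58.8 / 44.1 |
| 46 | 36 / 37 / 37 | 5.12 / 2.43 / 2.43 | 69.4 / 55.9 / 55.9 |
| 49 | 39 / 39 / 40 | 2.80 / 2.80 / 1.25 | 61.2 / 61.2 / 47.2 |
| 51 | 40 / 41 / 41 | 3.86 / 1.84 / 1.84 | 68.5 / 55.6 / 55.6 |

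Over all twelve sizes, error in the accepting direction is 2.8% to 5.6% (Wald), 1.3% to 3.0% (Wilson) and 1.05% to 2.43% (exact).

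**4. Total two-sided error at a true 66%.** This adds the chance that the interval lies wholly below 0.66.
- Wald: 4.95% to 7.94%; above 5% at ten sizes (all but n = 41 and 49, though n = 48 is only 5.04%).
- Wilson: 3.71% to 6.06%; above 5% at n = 43, 45, 46, 50 and 51.
- Clopper-Pearson: 2.63% to 4.39%; never above 5%.

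**5. How often the choice matters.** At the count nearest 80%, Wald accepts at all twelve sizes, Wilson at seven and exact at four (n = 46, 47, 50, 51). At a true 80%, Wald and exact disagree on acceptance with probability 12.7% to 15.6% at eleven sizes, and 29.8% at n = 42, where both 33 and 34 are discordant. At n = 51, 41/51 passes under all three (lower limits 0.695, 0.675, 0.669); 40/51 passes under Wald only (0.671, 0.654, 0.647).

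**The case against.** The method is named in advance and used consistently, and the stated half-width is labelled as an approximation, so the documents do not contradict themselves. That is true; the fault is that the rule misses its own alpha.

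The hypothesis is directional, so total error counts intervals wholly below 66%, which nobody would read as success. Counting wrong acceptances only, Wald exceeds 5% just at n = 42 and 46. That is fair if 5% is the benchmark. But a two-sided 95% interval allows 2.5% in the accepting tail, and Wald exceeds that at every size.

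A continuity correction may have been meant, since the stated 13 points lies between 12.4 without it and 13.6 with it. With it, total error is within 5% at eight of the twelve sizes. But the plan does not mention one, and 32/40 would still be accepted (lower limit 66.4%).

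The showcase is n = 40, the bottom of the range, and Wald behaves better elsewhere: its coverage at a true 80% is 90.5% at n = 40, 95.1% at n = 45 and 94.0% at n = 51. At a true 90%, Wald and exact disagree only 2.6% of the time at n = 40 and 0.7% at n = 51. This stands, and it limits the weight of the point. No planning rate is given for the secondary endpoint, so there the argument rests on the error rate alone.

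Finally, a feasibility pilot may reasonably fear wrong rejection more than wrong acceptance. If so, the plan should state a larger alpha openly.

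**Conclusion.** The concern holds, as a minor point. At n = 40 to 51 the planned interval does not keep the stated alpha, and at the result used to justify the sample size the acceptance comes from the interval formula alone. Against the exact rule the effect on acceptance is one count at eleven sizes and two at n = 42. The estimated proportion is unaffected. The documents attach no go/no-go decision to 66%, and section 2.1 already states: "The anticoagulation clinic intends to undertake a clinic-wide randomized quality improvement trial in the near future".

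The figures assume independent patients and an uncorrected Wald interval. Patients are grouped under 12 clinicians, and none of the intervals discussed allows for that.

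**What to change.** In 11.5.1 and 11.6.1, replace the normal approximation with one named 95% interval, used both for reporting and for the 66% decision. Clopper-Pearson is suggested because, under independence, it keeps total error below 5% and accepting-direction error at or below 2.43% at every planned size. Wilson removes most of the excess, but its total error still passes 5% at five sizes and its accepting-direction error is 2.6% to 3.0% at n = 42, 45 and 49. Do not report one interval and decide on the other: at 34/42, 36/45 and 39/49 Wilson excludes 0.66 (lower limits 0.667, 0.662, 0.664) and exact does not (0.659, 0.654, 0.657). The same sentence can say that acceptance requires the lower limit to lie above 0.66.

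Restate 11.1.1: 32/40 gives an exact 95% interval of 64% to 91%, and excluding 66% needs at least 33/40, or 41/51 at n = 51.

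The cost is three short text changes and no new data. The exact rule is conservative: acceptance at a true 80% falls from 59% to 44% at n = 40, from 68% to 38% at n = 42 (53% with Wilson) and from 69% to 56% at n = 51. The plan states no power, so no stated power is lost.

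### The acceptance rules for the primary and secondary endpoints omit the direction of the hypotheses, so an interval wholly below 0.66 also satisfies them

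*Combined protocol and SAP*

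**What the plan says.** Section 11.4.1 gives both Group 1 hypotheses a direction. For the primary endpoint it states that "the rate of participant recruitment and participation in assessment 1 (the primary endpoint) will exceed 66" per cent. For the secondary endpoint it says "we hypothesize that the rate of delivery of intended quality improvement strategies will exceed 66" per cent.

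Section 11.5.1 turns the first hypothesis into a decision rule: "We will accept this hypothesis if the two-sided confidence interval", at alpha 0.05, "for the primary endpoint excludes 0.66". Section 11.6.1 does the same for the second: "We will accept the hypothesis if the two-sided confidence interval (alpha=0.05) for the secondary endpoint excludes 0.66". Both intervals use the normal approximation to the binomial.

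Neither rule mentions the lower limit or asks that the interval lie above 0.66, and no other section adds this. Section 11.2.1 says only that proportions and confidence intervals will be calculated, and 11.1.1 deals only with precision.

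**The concern.** An interval can exclude 0.66 in two ways: by lying wholly above it or wholly below it. The hypotheses concern only the first, but the rules as written accept on either. A result showing that the rate is clearly under 66% would therefore formally lead to acceptance of the claim that it is over 66%.

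The wording covers both endpoints for which the plan states a hypothesis. The study exists to find out whether the procedures are feasible, so a rate well under 66% is a possible outcome, and that is where the rule gives the wrong answer.

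**Working it through.** **Inputs**
- Threshold 0.66, direction upward (11.4.1).
- Two-sided interval, alpha 0.05, normal approximation (11.5.1, 11.6.1).
- Expected completion rate 80% with n=40 (11.1.1).
- Group 1 size 40 to 51 patients (6.1.1).

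**The plan's own figure.** Section 11.1.1 says "we will be able to estimate a recruitment rate of 80% to within a 95% confidence interval of +/- 13" percentage points. The half-width is 1.96 × √(p(1−p)/n) = 1.96 × √(0.80 × 0.20/40) = 0.124, or 12.4 points. The stated 13 is this figure rounded up; a variance with divisor n−1 gives 12.55, and a t quantile on 39 degrees of freedom gives 12.8. The figure is reproduced to within one point, and nothing below depends on it.

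**Counts that satisfy the rule.** For each count k, the interval is k/n ± 1.96 × √((k/n)(1−k/n)/n).

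| n | Interval wholly below 0.66 | Next count up | Interval wholly above 0.66 | Next count down |
|---|---|---|---|---|
| 40 | k ≤ 20 (50.0%, 34.5% to 65.5%) | k=21, upper limit 0.680 | k ≥ 32 (80.0%, 67.6% to 92.4%) | k=31, lower limit 0.646 |
| 51 | k ≤ 26 (51.0%, 37.3% to 64.7%) | k=27, upper limit 0.666 | k ≥ 40 (78.4%, 67.1% to 89.7%) | k=39, lower limit 0.648 |

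The bracketed intervals are those at the boundary counts 20, 26, 32 and 40. For example, 20/40 gives 0.50 ± 1.96 × √(0.25/40) = 0.50 ± 0.155.

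**Probability of acceptance.** These are exact binomial sums over the counts above. Of the true rates shown, only 80% is the plan's assumption; the others show the range.

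| True rate | n=40: from below | n=40: from above | n=40: literal rule | n=51: from below | n=51: from above | n=51: literal rule |
|---|---|---|---|---|---|---|
| 0.80 | 0.00002 | 0.593 | 0.593 | 0.000003 | 0.685 | 0.685 |
| 0.66 | 0.027 | 0.040 | 0.067 | 0.019 | 0.039 | 0.058 |
| 0.60 | 0.130 | 0.006 | 0.136 | 0.121 | 0.004 | 0.125 |
| 0.50 | 0.563 | 0.0001 | 0.563 | 0.610 | <0.0001 | 0.610 |
| 0.40 | 0.926 | <0.0001 | 0.926 | 0.958 | <0.0001 | 0.958 |

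At the planned rate the two readings agree. Between 0.66 and 0.40, the literal rule is more likely to accept the further the true rate falls below the threshold, and almost all of those acceptances are in the wrong direction. The upward rule behaves as it should: its acceptance probability falls towards zero.

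**The case against.** The strongest reply is that the direction is already in the text. The rule in 11.5.1 refers back to the hypothesis stated immediately before it, which is that the rate is above 66%. Using a two-sided interval that excludes the null value is common shorthand for testing such a claim, with the side fixed by the claim itself. No sensible analyst would look at 20/40 and report a rate above 66%, and the estimate printed beside the verdict would expose the contradiction. The objectives are exploratory, no progression or stopping decision uses the rule, and the sample size rests on precision. The larger probabilities above also need true rates that the plan does not assume.

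All of this is fair, and it settles the weight of the point. It does not make the sentence correct: an acceptance criterion should be usable as written, and this one drops a condition that its hypothesis contains.

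Two limits on the arithmetic also stand. The binomial sums treat patients as independent, whereas delivery of the clinician-level strategies is clustered within 12 clinicians. And the analysed number may fall outside 40 to 51: 8.1.1 removes patients who stop warfarin or leave the service in the first five weeks, while 11.2.1 analyses everyone randomised. Clustering would alter the probabilities but not the cut-off counts at a given n; a different denominator would alter both. Neither affects the wording gap.

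**Conclusion.** The point holds and is minor. The decision rules in 11.5.1 and 11.6.1 are incomplete as written, although the intended test is clear from 11.4.1. Taken literally, they accept at 20/40 or fewer and at 26/51 or fewer, results that contradict the hypotheses. This has no practical effect if the true rate is near the planned 80%; it matters only if the rate is well below 66% and the rule is applied to the letter. These counts assume the plan's normal-approximation interval and denominators of 40 and 51. The probabilities also assume independent patients.

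**What to change.** In both 11.5.1 and 11.6.1, replace the condition that the interval excludes 0.66 with the condition that *the lower limit of the two-sided 95% confidence interval is greater than 0.66*.

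The new wording should not be described as a one-sided test at alpha 0.025. If the normal-approximation interval is kept, the exact probability of acceptance at a true rate of 66% is about 0.040 with n=40 and 0.039 with n=51.

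The cost is one phrase in each of two sections. The intended success cut-offs (32/40 and 40/51), the sample size, the interval method and the data collection all stay as they are.
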